13 ANALYSIS OF PERFORMANCE

13.1 Primary performance endpoint

The primary endpoint consists in the assessment of 25 % increase from Visit 1 (*Day 0 of treatment - baseline*) to Study Termination Visit (*Day 35 ± 4 of treatment*) of tear film break-up time with fluorescein (TFBUT)^ø. The data will be reported (change vs baseline) as minimum, maximum, mean, standard deviation or median and IQR. According to the data distribution, paired t-test or Wilcoxon signed-rank test will be used to test the statistical significance of the change from baseline to each time points. [Time frame: Visit 1, and Study Termination Visit].

Patients with a Tear Film Break-up Time TFBUT test ≤ 10 in the study eye (study eye) at the screening visits are eligible for enrollment.

TFBUT will be measured by determining the time to tear break-up. The TFBUT will be performed after instillation of 5 μl of 2% preservative-free sodium fluorescein solution into the inferior conjunctival cul-de-sac of each eye. The patient will be instructed to blink several times to thoroughly mix the fluorescein with the tear film. To achieve maximum fluorescence, the examiner should wait approximately 30 seconds after instillation before evaluating TFBUT.

With the aid of a slit lamp at 10X magnification using cobalt blue illumination, the examiner will monitor the integrity of the tear film, noting the time it takes to form lacunae (clear spaces in the tear film) from the time that the eye is opened after the last blink. This measurement will be performed within 10 seconds maximum. The TFBUT will be measured twice during the first minute after the instillation of the fluorescein. The TFBUT value will be the average of 3 measurements.

13.2 Secondary objective

The secondary objectives were:

Clinical Performance

- Changes in NEI score from baseline will be summarized as minimum, maximum, mean,

Study code: 052/SI Hyalistil Bio PF Mono

standard deviation or median and IQR. Paired t-test or Wilcoxon signed-rank test will be used to test the statistical significance of the change from baseline to each timepoints. [Time frame: Visit 1, Visit 2 and Study Termination Visit].

The cornea is divided into five sectors (central, superior, inferior, nasal and temporal), each of which is scored on a scale of 0–3, with a maximal score of 15. Both nasally and temporally, the conjunctiva is divided into a superior paralimbal area, an inferior paralimbal area and a peripheral area with a grading scale of 0–3 and with a maximal total score of 18 for the nasal and temporal conjunctiva.

For a better reading it is also essential not to use an intense illumination beam, which may reduce the contrast and lead to an underestimation of grading.

- Changes in TFBUT from baseline will be reported as minimum, maximum, mean standard deviation or median and IQR. Paired t-test or Wilcoxon signed-rank will be used to test the statistical significance of the change from baseline to each timepoints. [Time frame: Visit 2, and Study Termination Visit].
- Change in the BVCA scores will be summarized as minimum, maximum, mean, standard deviation or median and IQR. Paired t-test or Wilcoxon signed-rank test will be used to test the statistical significance. Details of changes (i.e., difference in BVCA scores between baseline and end of treatment) will be summarized as well. [Time frame: Visit 1, Visit 2 and Study Termination Visit].
- Best Corrected Visual Acuity BCVA was measured using the standard Early Treatment Diabetic Retinopathy Study (ETDRS) acuity chart lighting, and procedures and reported in Best-corrected visual acuity is measured at all trial visits using standard charts, (chart 1 is used for testing the visual acuity of the RIGHT eye; Chart 2 for testing the LEFT eye). Patients should not be allowed to see any of the charts before the examination.
A distance of 4 meters is required between the patient's eyes and the visual acuity chart. With the box light off, not more than 15 foot-candles of light (161.4 Lux) should fall on the center of the chart. To measure the amount of light, the room is set up for visual acuity testing, but with the box light off. The light meter is placed at the fourth line from the top of the chart, with its back against the chart and the reading is taken. If more than one line available for testing visual acuity, the visual acuity of an individual patient should be measured in the same line at each visit, if possible. If different lines are used to test visual acuity, they must each meet the same standards.

Patient reported outcomes:

- Change in the SANDE scores will be summarized as minimum, maximum, mean, standard deviation or median and IQR. Paired t-test or Wilcoxon signed-rank test will be used to test the statistical significance. Details of changes (i.e., difference in SANDE scores between

Study code: 052/SI Hyalistil Bio PF Mono

baseline and end of treatment) will be summarized as well. [Time frame: Visit 1, Visit 2 and Study Termination Visit].

The SANDE questionnaire is a short questionnaire to evaluate both the intensity and frequency of dry eye using a 100 mm VAS. The patient's symptoms of ocular dryness and/or irritation will be quantified on the scale based on two questions assessing both severity and frequency of symptoms. For the assessment, patients mark the point that they feel represents their perception of their current state on the 100 mm VAS line. The VAS score is determined by measuring in millimeters from the left-hand end of the line to the point that the patient marks. The SANDE scores will be then evaluated for the 2 questions severity (0-100) and frequency (0-100). To simplify the procedure the patient will be informed that to provided anchors for the question measuring the frequency of symptoms, the extreme left of the 100 mm line indicated "rarely" and the extreme right indicated "all of the time". Similarly, for the question that measured the severity of symptoms, the words "very mild" and "very severe" were placed at the left and right ends of the 100 mm line, respectively.

At each visit, only one assessment is performed aggregating the situation for both eyes (i.e. no separate assessment per study eye).

Data collected from the SANDE questionnaire were calculated by multiplying the frequency score by the severity score and obtaining the square root.

- VAS will be summarized reporting the number of patients and related percentage in each category. [Time frame: Study Termination Visit].

Patients will be asked to rate their degree of satisfaction to the treatment and answer the following questions:

- "I feel satisfied using this treatment? ",
- "With this treatment, I have a feeling of freshness?",
- "With this treatment, I have a feeling of relief?",
- "This treatment contributed to reduce my pain due to eye dryness?",
- "This treatment is comfortable? ",

Patients will be asked to place a vertical mark on a horizontal line, from 0 to 100 mm, to indicate the degree of satisfaction to the treatment, where:

- ✓ 0-10 mm=none
- ✓ 11-30 mm=very mild
- ✓ 31-50 mm=mild
- ✓ 51-70 mm=moderate
- ✓ 71-90 mm=strong
- ✓ 91-100 mm=very strong.

- Changes from baseline in DEQS for each subscale and total score will be summarized as minimum, maximum, mean, standard deviation or median and IQR. Paired t-test or Wilcoxon signed-rank test will be used to test the statistical significance of the change from baseline to the study termination. [Time frame: Visit 1 and Study Termination Visit].

Study code: 052/SI Hyalistil Bio PF Mono

The DEQS questionnaire consists of 15 questions divided in two subscales: the Bothersome Ocular Symptoms (six questions) and the Impact on Daily Life (nine questions). Each question is assessed using two-step scales. The first step is to assess the frequency of symptoms and disability, and the second is to assess the degree of severity. The frequency is scored on a 5-point Likert scale ranging from 0 to 4 (0 = never, 4=always). When the answer was “never,” then the respondent could skip to the next question; but when any frequency was reported (1–4), the respondent had to rate the degree of severity, which was scored on a 4-point Likert scale ranging from 1 to 4, with a larger number indicating a greater burden.

The total score of the answer will be calculated using the summation of the degree scores of all questions answered multiplied by 25 and divided by the total number of questions answered. The total score ranging from 0 to 100, with a higher score, represented greater disability.

$$\text{Total summary score} = \frac{(\text{Sum of the degree scores for all questions answered} \times 25)}{\text{Total number of questions answered}}$$

Subscale scores will be calculated similarly, using only the item from each subscale.

- GENERAL EYES STATUS (GES) will be summarized as minimum, maximum, mean, standard deviation or median and IQR. Paired t-test or Wilcoxon signed-rank test will be used to test the statistical significance of the change from baseline to the study termination. [Time frame: Visit 1 and Study Termination Visit].

GENERAL EYES STATUS will be assessed using the degree scores of a question answered using the 6-point scale:1= Estremamente bene, 2 = Molto bene, 3 = Bene, 4 = Male, 5= Molto male and 6= Estremamente male.

Safety Evaluation:

- IGAS will be summarized reporting the number of patients and related percentage in each category. [Time frame: Study Termination Visit].

The Safety of medical device will be assessed using the Investigator Global Assessment of Safety (IGAS): using the 4-point scale:1= very good safety, 2 =good safety, 3 = moderate safety and 4 = poor safety. IGAS will be evaluated during the Study Termination Visit. [Time Frame: Study Termination Visit].

- Incidents will be coded using the last updated version of the MedDRA dictionary to give a preferred term (PT) and a system/organ class term (SOC) for each event. The number of patients who experienced at least one incident, study product-related incidents, serious incidents, and the number of patients withdrawn due to an incident will be summarized. The frequency of incidents will be presented overall, by SOC and PT, and additional grouping by severity and relationship to the observed treatment will be performed. [Time Frame: During the treatment period].

- Changes from baseline in IOP will be summarized as minimum, maximum, mean, standard deviation or median and IQR. Paired t-test or Wilcoxon signed-rank will be used to test the statistical significance of the change from baseline to each timepoints. [Time frame: Visit 1, Visit 2 and Study Termination Visit].

Intraocular pressure (IOP) measurement was performed using a Goldmann applanation tonometer after topical anesthesia with unpreserved 0.4% oxybuprocaine hydrochloride.

Moreover, for each endpoint, a delta % calculation will be performed.

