§ Restitution of the amount of used single dose containers and empty/unused medical device boxes returned by patients to the centre.

'In case of premature study discontinuation, patients will undergo an Early Termination Visit (ETV). During the ETV the patients will return the amount of used single dose containers and empty/unused medical device boxes returned by patients to the centre'

* The "unique subject identifiers code" consists of the 5-digit screening number (e.g. S1001, S1002,...S1028 etc.), and, if applicable, the 4-digit subject clinical investigational number (e.g. 1001, 1002,...1028 etc.). Specifically, the first subject clinical investigational number was referred to the study site.

Allocation screening number and subject clinical investigational number are separated by slashes (e.g. "S1001/1001"). (e.g. "S1001/1001" for site number 1, "S2001/2001" for site number 2).

† The TFBUT value will be recorded as the average of 3 measurements.

19. Primary and secondary outcomes[^]

Primary Endpoints[#]

- *Clinical performance:*

-25 % increase from Visit 1 (*Day 0 of treatment - baseline*) to Study Termination Visit (*Day 35 ± 4 of treatment*) of tear film break-up time with fluorescein (TFBUT)f. [Time frame: Visit 1 and Study Termination Visit].

Secondary Endpoints

- Reduction from baseline (*Visit 1- Day 0 of treatment*) in the corneal and conjunctival fluorescein staining score using the NEI scale.

Fluorescein staining of the ocular surface is assessed as the total sum of the corneal and conjunctival subregions.

- Corneal Fluorescein Staining (NEI score, sum of 5 subregions, maximum score 15. Each subregion will have a maximum score of 3.

(0=no staining, 3 = maximum staining).

- Conjunctival Fluorescein Staining (NEI score, sum of 6 subregions, maximum score 18. Each subregion will have a maximum score of 3.

(0=no staining, 3 = maximum staining).

[Time frame: Visit 1, Visit 2 and Study Termination Visit].

- Tear film break-up time with fluorescein (TFBUT)[◊]. [Time frame: Visit 2 and Study Termination Visit].

- BCVA is measured using the standard Early Treatment Diabetic Retinopathy Study (ETDRS) acuity chart and reported in ETDRS letters. [Time frame: Visit 1, Visit 2 and Study Termination Visit];

- *Patient reported outcomes:*

- Change in intensity and frequency of dry eye symptoms assessed by completing the questionnaire SANDE. [Time frame: Visit 1, Visit 2 and Study Termination Visit].

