- Change in the BVCA scores will be summarized as minimum, maximum, mean, standard deviation or median and IQR. Paired t-test or Wilcoxon signed-rank test will be used to test the statistical significance. Details of changes (i.e., difference in BVCA scores between baseline and end of treatment) will be summarized as well. [Time frame: Visit 1, Visit 2 and Study Termination Visit].

Study code: 052/SI Hyalistil Bio PF Mono

- IGAS will be summarized reporting the number of patients and related percentage in each category. [Time frame: Study Termination Visit].
- Incidents will be coded using the last updated version of the MedDRA dictionary to give a preferred term (PT) and a system/organ class term (SOC) for each event. The number of patients who experienced at least one incident, study product-related incidents, serious incidents, and the number of patients withdrawn due to an incident will be summarized. The frequency of incidents will be presented overall, by SOC and PT, and additional grouping by severity and relationship to the observed treatment will be performed. [Time Frame: During the treatment period].
- Changes from baseline in IOP will be summarized as minimum, maximum, mean standard deviation or 18 median and IQR. Paired t-test or Wilcoxon signed-rank will be used to test the statistical significance of the change from baseline to each timepoints. [Time frame: Visit 1, Visit 2 and Study Termination Visit].
- Changes from baseline in DEQS score will be summarized as minimum, maximum, mean, standard deviation or median and IQR. Paired t-test or Wilcoxon signed-rank test will be used to test the statistical significance of the change from baseline to the study termination. [Time frame: Visit 1 and Study Termination Visit].

24. Data collection – eCRFs

An electronic data capture system will be used for this study. An electronic CRF (eCRF) is designed to collect all the data required by the clinical investigation plan and collected by the investigator for each patient.

The Investigator must ensure that the clinical data required by the clinical investigation plan, collected during the study, are carefully reported, in the eCRFs. He must also check that the data reported in the eCRFs correspond to those in the patients' source documents.

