4. CLINICAL INVESTIGATION DESIGN

This clinical investigation is a multicentric prospective observational open-label, non-interventional clinical investigation evaluation, during the conventional clinical practice, the performance and safety of the daily instillation of Hyalistil Bio PF device in the treatment of patients affected by eye *discomfort* in particular in case of ocular dryness.

The clinical evaluation period was run approximately for 4 months from first patient first visit (FPFV) March 14th, 2023, to last patient last visit (LPLV) August 3rd, 2023. All patients were followed from enrolment until study end date, which was occur when, in compliance with the normal clinical practice, the last patient was undergo the Study Termination Visit (35± 4 days from the first instillation of study product).

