6.2. Final Analysis

Final analysis will be performed according to the current version of the protocol (version 2 of March 14th, 2023) and to this Statistical Analysis Plan (version 1 of October 10th, 2023), after data cleaning operations and Data Base (DB) Lock will be performed.

The statistical analysis will be performed using SAS 9.4 for Windows (SAS Institute Inc., Cary, NC, USA).

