14. CHANGES IN THE PLANNED ANALYSES

No deviations in the conduct of the study or the planned analysis are anticipated. Should any deviations from the analyses specified in the authorized statistical analysis plan arise, such deviations will be documented in the final clinical study report.

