5 PERFORMANCE DATA (SECONDARY ENDPOINTS)

-NEI Scale ITT population

Table 5.1.1 TOTAL SCORE NEI ITT population (v1) vs (v3)

Table 5.2.1 TOTAL SCORE NEI ITT population (v1) vs (v2)

Table 5.3.1 TOTAL SCORE CORNEA ITT population (v1) vs (v3)

Table 5.3.2 TOTAL SCORE CORNEA ITT population (v1) vs (v2)

Table 5.4.1 TOTAL SCORE CONJUNCTIVA ITT population (v1) vs (v3)

Table 5.4.2 TOTAL SCORE CONJUNCTIVA ITT population (v1) vs (v2)

-TFBUT ITT POPULATION

Table 5.5.1 TFBUT ITT population (v1) vs (v2)

-Questionnaire SANDE ITT population

Table 5.6.1 TOTAL SCORE SANDE ITT population (v1) vs (v3)

Table 5.7.1 TOTAL SCORE SANDE ITT population (v1) vs (v2)

Study code: 052/SI Hyalistil Bio PF Mono

Table 5.8.1 SEVERITY DRYNESS/IRRITATION ITT population (v1) vs (v3)

Table 5.8.2 SEVERITY DRYNESS/IRRITATION ITT population (v1) vs (v2)

Table 5.9.1 FREQUENCY DRYNESS/IRRITATION ITT population (v1) vs (v3)

Table 5.9.2 FREQUENCY DRYNESS/IRRITATION ITT population (v1) vs (v2)

-Questionnaire VAS ITT population

Table 5.10.1 Question "I feel satisfied using this treatment? ", ITT population

Table 5.10.2 Question "With this treatment, I have a feeling of freshness?", ITT population.

Table 5.10.3 Question "With this treatment, I have a feeling of relief?", ITT

Table 5.10.4 Question "This treatment contributed to reduce my pain due to eye dryness?", ITT population

Table 5.10.5 Question "This treatment is comfortable? ", ITT population

Table 5.10.6 Total score VAS, ITT population

-DEQS ITT POPULATION

Table 5.11.1.1 DEQS Summary score ITT population (v1) vs (v3)

Table 5.11.2.1 DEQS Bothersome Ocular Symptoms subscale ITT population (v1) vs (v3)

Table 5.11.3.1 DEQS Impact on Daily Life subscale ITT population (v1) vs (v3)

Table 5.11.4.1 DEQS-GES ITT population (v1) vs (v3)

-IGAS

Table 5.12.1 IGAS ITT populations

-IOP ITT POPULATION

Table 5.13.1 IOP ITT population (v1) vs (v3)

Table 5.14.1 IOP ITT population (v1) vs (v2)

Study code: 052/SI Hyalistil Bio PF Mono

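### SAP version 1, dated after the last visit of an open-label study, places three unplanned significance tests and an underived VAS total among the secondary endpoint tables without recording them as additions to the protocol

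*SAP*

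**What the plan says.** **Timing.** SAP 4 runs the study from 14 March 2023 "to last patient last visit (LPLV) August 3rd, 2023". SAP 6.2 identifies itself as "this Statistical Analysis Plan (version 1 of October 10th, 2023" and places the final analysis after data cleaning and database lock. SAP 1.1 records no earlier SAP. SAP 4.3 states that the study is open-label.

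**Protocol version 2.** Section 20 describes the DEQS as 15 items, six on symptoms and nine on daily life, giving one score from 0 to 100. Section 23 plans one analysis of it: "Changes from baseline in DEQS score will be summarized as minimum, maximum, mean, standard deviation or median and IQR". The satisfaction VAS is to be tabulated by category. General Eyes Status does not appear.

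**SAP.** Section 13.2 says of the DEQS: "Changes from baseline in DEQS for each subscale and total score will be summarized as" (the usual statistics), with a paired test. It then adds General Eyes Status: "GENERAL EYES STATUS will be assessed using the degree scores of a question answered using the 6-point scale", also with a paired test. The secondary part of the table list in SAP 15.2 holds tables for the two subscales (5.11.2.1 and 5.11.3.1) and for General Eyes Status (5.11.4.1), and "Table 5.10.6 Total score VAS, ITT population". SAP 14 opens: "No deviations in the conduct of the study or the planned analysis are anticipated".

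**The concern.** The protocol is the only record in these documents of what was to be analysed before the data were collected. The study has one treated group and no masking, so anyone with access to the data can see changes from baseline as they accrue. An analysis first written down after the last visit cannot carry the weight of a pre-specified secondary result, whatever the reason for its late appearance.

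The SAP gives the reader no means of telling the two kinds apart. The added tables share a heading and a layout with the planned ones. SAP 10 calls any p-value below 0.05 significant, and SAP 10.4 adjusts for multiplicity only when necessary, without saying when that is. SAP 14 commits to reporting departures from the SAP, so an addition already written into the SAP would not trigger disclosure. A significant General Eyes Status or subscale result could then be reported on the same footing as the protocol's DEQS score.

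**Working it through.** The documents print no figure of their own on this point. The check is a date difference, a comparison of the two texts, and a count.

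**Dates.** From 3 August to 10 October 2023: 28 days to the end of August, 30 in September and 10 in October, giving 28 + 30 + 10 = 68 days.

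**Comparison.**

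| Item | Protocol version 2 | SAP 5.2 endpoint list | SAP 13.2 | SAP 15.2, secondary tables |
|---|---|---|---|---|
| General Eyes Status | absent | absent | paired test | 5.11.4.1 |
| DEQS symptom subscale | items described, no score or test | absent | paired test | 5.11.2.1 |
| DEQS daily life subscale | items described, no score or test | absent | paired test | 5.11.3.1 |
| VAS total | absent; categories only | absent | absent; categories only | 5.10.6 |
| Corneal and conjunctival staining | both named, maxima 15 and 18, three visits | same as protocol | NEI score test; both regions described | 5.3.1 to 5.4.2 |

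The first four rows are additions. The last is not. SAP 9.1 lists five VAS variables and no total, and nothing says how a total would be formed. The only p-values in the shell of Table 5.10.6 are for normality, so it adds no test of effect.

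**Count of tests against baseline, one per table.**
- Performance tables under the secondary heading: NEI 6 + TFBUT 1 + SANDE 6 + DEQS and General Eyes Status 4 = 17.
- With the two IOP tables under the same heading: 17 + 2 = 19.
- Added tests: General Eyes Status 1 + DEQS subscales 2 = 3.
- Without them: 17 − 3 = 14 performance tests, or 19 − 3 = 16 with IOP.

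**Illustrative error rate.** For k independent tests at 0.05 with no true change, the chance of at least one p < 0.05 is 1 − 0.95^k.
- k = 3: 1 − 0.857 = 0.143, about 14%.
- Whole list: 0.62 for k = 19, falling to 0.56 for k = 16.

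The scores are correlated, so these figures are rough guides only.

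**When General Eyes Status was collected.** SAP 9.1 lists it with the DEQS fields of the CRF. The last CRF release in SAP 1.3 is dated 24 July 2023, 10 days before the last visit. The documents do not show in which release the item first appeared. The planned test needs a Visit 1 value, and an in-window final visit on 3 August implies a first instillation no later than 31 days before, on 3 July. Any Visit 1 value recorded on schedule therefore predates the SAP by about three months.

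**The case against.** The strongest case on the other side has four parts.

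1. *Nothing shows that the choice was driven by data.* This stands. Database lock was still ahead, no analysis is reported, and General Eyes Status was a CRF item. A reader might infer from the dates that outcomes were picked after results were seen; the documents do not support that. They show only that the analysis was written down late.

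2. *The staining components are in the protocol.* This stands. A reader might take one sentence of Protocol 19, "Fluorescein staining of the ocular surface is assessed as the total sum of the corneal and conjunctival subregions", to mean that separate corneal and conjunctival tests are also new. That would make seven additions, and 1 − 0.95^7 = 30%. But the same endpoint names both scores, with their ranges and all three visits as time frame. Protocol 23 plans a test of the NEI score without saying whether the parts are tested separately, which is an ambiguity and not a new outcome.

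3. *The headings do not assign rank.* This stands in part. SAP 3.2 and 5.2 include neither General Eyes Status nor the VAS total, and the secondary table list also holds IGAS and IOP, which SAP 5.3 treats as safety. So the SAP does not formally promote these items. It leaves their rank unclear, and the report tables would follow the heading.

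4. *SAP 14 looks forward.* This stands. It speaks of departures from the SAP and does not certify that SAP and protocol agree. Reading it as a denial that anything was added goes too far. Even so, the additions are recorded as such nowhere in the SAP.

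The DEQS subscales are also a milder case than General Eyes Status, being new analyses of a planned questionnaire along a division the protocol already describes.

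**Conclusion.** The concern holds in a limited form. Three significance tests (General Eyes Status and two DEQS subscales) and one underived, untested VAS total are absent from protocol version 2. They first appear in a SAP dated 68 days after the last visit, stand among the secondary endpoint tables, and are not identified as additions. The 14% figure assumes independent tests, all null, each judged at 0.05; the true figure depends on correlations that the documents do not give.

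The primary endpoint and the protocol's own secondary endpoints are unaffected. What changes is which results may be called pre-specified secondary findings. The documents support neither a claim that results had been seen nor a count that includes the corneal and conjunctival tests.

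**What to change.** - Move General Eyes Status, the two DEQS subscales and the VAS total to a section headed *Exploratory, analysis not in protocol version 2, specified after last patient last visit*. Report them descriptively, without significance claims.
- Define the VAS total or drop Table 5.10.6.
- List these additions in SAP 14 as changes from protocol version 2, and carry the list into the clinical study report.
- Keep the corneal and conjunctival scores as components of the protocol's NEI staining endpoint, with the total as the secondary endpoint result. Labelling them as defined after the last visit would be wrong.

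The cost is wording in the SAP and report. No new data are needed and every result is still shown. The downside is that fewer results can be described as secondary endpoint findings.
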